#### 4.1.1 Randomised Study Design

Prior to CSP V3.0, approximately 56 patients were planned to be randomised in a ratio of 1:1 to receive treatment with CCI savolitinib CCI plus CCI osimertinib CCI or CCI savolitinib CCI plus placebo. At least half of the patients randomised into the study will be second-line patients who were treated with osimertinib as first-line therapy. Randomisation will be stratified according to the number of prior lines of therapy (ie, osimertinib monotherapy as first line or  $\geq$  second line [which includes patients who received osimertinib monotherapy before or after chemotherapy]).

Prospective testing of tumour specimens to determine MET amplification by central FISH using tumour specimens collected after progression on prior treatment with osimertinib should be performed at Pre-screening in advance of Screening for the main study. Patients determined to be MET amplified in Pre-screening will undergo screening during the 28 days prior to randomisation to confirm eligibility ([Sections 5.1](#) and [5.2](#)).

Provision of a FFPE tumour specimen is mandatory (refer to the Laboratory Manual for detailed specimen requirements). This will be used for prospective analysis of MET amplification by FISH.

Patients will continue to receive study medication CCI in 28-day cycles until objective PD by RECIST 1.1 is assessed, unacceptable toxicity occurs, consent is withdrawn or another discontinuation criteria is met ([Section 7](#)). At the time of investigator assessment per RECIST 1.1 of PD, the randomisation blind can be broken and patients who were initially randomised to the savolitinib plus placebo arm will be given the opportunity to cross-over (see [Sections 4.1.2](#) and [6.3](#)). Patients originally randomised to savolitinib plus osimertinib may continue to receive treatment with savolitinib plus osimertinib or osimertinib monotherapy (if savolitinib was stopped earlier) beyond RECIST 1.1 defined PD as long as they continue to receive clinical benefit, in the opinion of the investigator, and do not meet any of the

discontinuation criteria. No other anti-cancer agent is permitted in combination with osimertinib within this study. Patients can continue on savolitinib monotherapy (if randomised to the savolitinib plus placebo arm or if osimertinib was stopped earlier) until objective PD by RECIST 1.1 is assessed. Savolitinib monotherapy post-progression is not permitted.

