#### 9.4.1 General Considerations

Descriptive statistics will be used for all variables as appropriate and will be presented by treatment arm. Continuous variables will be summarised by the number of observations, mean, standard deviation, median, minimum, and maximum. Categorical variables will be summarised by frequency counts and percentages for each category. Unless otherwise stated, percentages will be calculated out of the population total for the corresponding treatment arm.

Results of all statistical analyses will be presented using a 95% CI and p-value, unless otherwise stated.

Additional subgroup analyses of efficacy and safety may be performed and will be specified in the SAP.

Depending on the extent of any impact, summaries of data relating to patients diagnosed with COVID-19, and impact of COVID-19 on study conduct (in particular missed visits, delayed or discontinued study intervention, and other protocol deviations) may be generated. More detail will be provided in the SAP.

Baseline for patients on randomised treatment will be the last assessment of the variable under consideration prior to the intake of the first dose, except for efficacy variables. For efficacy variables, baseline is defined as the last visit prior to randomisation. For patients who cross-over from savolitinib plus placebo to savolitinib plus osimertinib, their data will be cut off for the purposes of any savolitinib plus placebo assessment at the last assessment of the variable under consideration prior to the intake of the first dose of the combination therapy.

Efficacy data will be summarised and analysed on the FAS, safety data will be summarised on the SAS and PK data will be summarised on the PK Analysis Set.

Baseline for ORR, PFS, DoR and tumour size assessments of patients who cross-over to savolitinib plus osimertinib from savolitinib plus placebo will be the progression scan on savolitinib plus placebo, acquired within 28 days of the start of treatment in the cross-over period. CCI

Baseline for safety assessments of patients who cross-over to savolitinib plus osimertinib from savolitinib plus placebo will be set as the last assessment prior to first dose of osimertinib.

A Cross-over Analysis Set is included for patients randomised to savolitinib plus placebo who cross-over to savolitinib plus osimertinib upon objective PD per RECIST 1.1.

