#### **9.4.3 Safety**

Safety and tolerability will be assessed in terms of AEs, SAEs, discontinuation rate due to AEs, deaths, laboratory data, vital signs, ECHO data, ECG data and ECOG performance status. All safety analyses will be performed on the SAS. Data will also be presented separately for patients who crossed over to savolitinib plus osimertinib upon investigator-assessed PD per RECIST 1.1 on savolitinib plus placebo. Safety data will be presented using descriptive statistics unless otherwise specified.

Adverse events will be coded using the most recent version of MedDRA that have been released for execution at AstraZeneca. Adverse events will be graded according to the National Cancer Institute CTCAE (Version 5.0).

The number of patients experiencing each AE will be summarised by the MedDRA system organ class, preferred term and treatment group. The number and percentage of patients with AEs in different categories (eg, causally related, CTCAE Grade  $\geq 3$  etc) will be summarised, and events in each category will be further summarised by MedDRA system organ class, preferred term and treatment group. If there are sufficient SAEs, they will be summarised separately. Further details will be provided in the SAP.

Adverse events occurring prior to the start of study intervention, treatment-emergent AEs and post-treatment emergent AEs will be presented separately. Adverse events occurring in the savolitinib in combination with placebo group will be split into 2 presentations based on whether they occurred before or after the crossover into the savolitinib in combination with osimertinib group.

Any AE occurring before the first dose of study intervention will be included in the data

listings but will not be included in the summary tables of AEs. Adverse event summary tables will include only treatment-emergent AEs. The following events are considered treatment emergent:

- Adverse events with an onset date on or after the first dose of randomised study intervention and within the safety follow-up period (28 days [ $\pm$  7 days] after last dose of all study intervention). Any events in this period that occur after a patient has received further therapy for cancer (following discontinuation of all study intervention) will be flagged in the data listings.
- Worsening of pre-existing events on or after the first dose of study intervention and within the safety follow-up period.

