Any events in this period that occur after a patient has received further therapy for cancer (following discontinuation of all study intervention) will be flagged in the data listings, but not included in the summaries.

An overview of AEs will present for each treatment group the number and percentage of patients with any AE, AEs with outcome of death, SAEs, and AEs leading to discontinuation of study intervention, as well as AEs leading to study intervention dose interruptions, and AEs leading to study intervention dose reduction as well as the number of individual occurrences in those categories.

Separate AE tables will be provided taken into consideration relationship as assessed by the investigator, CTCAE grade, seriousness, death and events leading to discontinuation of study intervention for the first 6 weeks and at any time as well as other action taken related to study intervention.

An additional table will present number and percentage of patients with most common AEs. Most common (eg, frequency of  $> x\%$ ,  $\geq x\%$ ) will be defined in the SAP.

In accordance with the requirements of the FDA, a separate table will present non-serious AEs occurring in more than 5% of patients in any treatment group.

Key patient information will be presented for patients with AEs with outcome of death, SAEs, and AEs leading to discontinuation of study intervention.

An AE listing for the SAS will cover details for each individual AE; an AE listing for patients who were not exposed to study intervention is presented separately.

Full details of AE analyses will be provided in the SAP.

During the evaluation of the AE data, an AstraZeneca medically qualified expert will review

the list of AEs that were not reported as SAEs or AEs leading to discontinuation. Based on the expert's judgement, significant AEs of particular clinical importance may, after consultation with the Global Patient Safety Physician, be considered other significant AEs and reported as such in the CSR. A similar review of laboratory/vital signs (pulse and BP)/ECG data will be performed for identification of other significant AEs. Examples of these could be marked haematological and other laboratory abnormalities, and certain events that lead to intervention (other than those already classified as serious), dose reduction or significant additional treatment. Tables and figures for potential Hy's Law cases will be produced.

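### The crude 'at any time' adverse event percentages in 9.4.3 can cover a longer window for savolitinib plus osimertinib than for savolitinib plus placebo patients who cross over

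*Supplement*

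**What the plan says.** **The window.** Section 9.4.3 defines treatment-emergent events as "Adverse events with an onset date on or after the first dose of randomised study intervention and within the safety follow-up period". The follow-up period runs to 28 days (± 7) after the last dose of all study intervention.

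**Combination arm.** Section 4.1.1 says: "Patients originally randomised to savolitinib plus osimertinib may continue to receive treatment with savolitinib plus osimertinib or osimertinib monotherapy", and this may go on "beyond RECIST 1.1 defined PD as long as they continue to receive clinical benefit". Post-PD treatment and the 28-day tail both fall inside the window.

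**Placebo arm.** Section 4.1.1 also says: "Savolitinib monotherapy post-progression is not permitted". Events in this arm are "split into 2 presentations based on whether they occurred before or after the crossover into the savolitinib in combination with osimertinib group" (9.4.3). For patients who cross over, section 9.4.1 adds that "their data will be cut off for the purposes of any savolitinib plus placebo assessment at the last assessment of the variable under consideration" before the first combination dose. Section 4.1.2 asks for cross-over within 28 days of the progression scan, with savolitinib continued meanwhile. Sections 4.1.2 and 4.1.4 also offer cross-over to patients without PD once the study is unblinded. Placebo-arm patients who never cross over keep the full window.

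**The summary.** "An overview of AEs will present for each treatment group the number and percentage of patients with any AE" (9.4.3). Some tables are given for the first 6 weeks as well as at any time. Duration of exposure is summarised, but it is not named as a denominator for AE rates.

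**The concern.** A crude percentage of patients with an event rises with the length of time over which events are counted. Here the rules let that time run past PD plus 28 days in one arm. In the other, for anyone who crosses over, it stops at the first combination dose. Such a patient contributes neither a post-PD treatment phase nor a 28-day tail to the randomised-phase table.

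Safety and tolerability of the two regimens is a stated objective, and the by-arm percentages are how it will be read. If the arms had the same event hazard, the overview and the at-any-time tables could still show more AEs, SAEs and discontinuations on the combination. A reader would naturally take that excess as the toxicity cost of adding osimertinib.

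**Working it through.** The documents give no AE incidence, no share crossing over and no amount of post-PD treatment, so there is no stated figure to reproduce. The size below is an illustration.

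**Inputs from the protocol**
- Combination window: time to PD + post-PD treatment + 28 days (4.1.1, 9.4.3).
- Placebo-arm window, patient crossing over at PD: time to PD + g, with g from 0 to 28 days (4.1.2, 9.4.3).

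**Assumed inputs**
- Same constant hazard h of a first event in both arms: 0.05 or 0.10 per month.
- Time to PD exponential with median 4 months in both arms, capped at 18 months. For context, section 2 quotes about 3 to 6 months for platinum chemotherapy after an EGFR-TKI.
- Half of combination patients treated past PD for an exponential time with median 2 months (mean 2/ln 2 = 2.885).
- All placebo-arm patients cross over.

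**Formula.** P(event) = 1 − E[exp(−h × window)]. With independent components the expectation is a product of factors, using 28 days = 28/30.4375 = 0.92 month.

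| Factor | h = 0.05 | h = 0.10 |
|---|---|---|
| Time to PD | 0.7801 | 0.6368 |
| 28 days, exp(−0.92h) | 0.9550 | 0.9121 |
| Post-PD treatment, 0.5 + 0.5/(1 + 2.885h) | 0.9370 | 0.8880 |

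**Combination**
- h = 0.05: 1 − 0.7801 × 0.9550 × 0.9370 = 30.2%.
- h = 0.10: 1 − 0.6368 × 0.9121 × 0.8880 = 48.4%.

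**Placebo arm and gap**

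| Cross-over after PD | h = 0.05 | Gap | h = 0.10 | Gap |
|---|---|---|---|---|
| Day 0 | 22.0% | 8.2 | 36.3% | 12.1 |
| Uniform over days 0 to 28 | 23.8% | 6.4 | 39.2% | 9.3 |
| Day 28 | 25.5% | 4.7 | 41.9% | 6.5 |

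The true hazard ratio is 1 in every cell.

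**Sensitivity**
- *No post-PD treatment.* The combination shows 25.5% and 41.9%. The gaps are 3.5 and 5.6 points with cross-over at day 0, 1.7 and 2.8 with uniform timing, and 0 at day 28.
- *Cap at 9 months*, the current interval from last randomisation to the final data cut-off. The gaps run from 4.9 to 8.5 points (h = 0.05) and 6.8 to 12.6 points (h = 0.10), so the cap does not drive the result.
- *Median time to PD of 3 to 6 months, half treated a mean of 3 months past PD.* A placebo-arm 30% corresponds to 34.0% to 43.4% on the combination.
- *Lower cross-over uptake.* The gap shrinks, because patients who do not cross over keep the 28-day tail.
- *First 6 weeks.* The first scheduled scan is at week 6 (± 7 days), so cross-over for PD before then should be uncommon and the artefact is essentially nil.

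**Check of the remedy.** With constant hazard, expected first events divided by expected time at risk is (1 − E[exp(−hW)]) / ((1 − E[exp(−hW)])/h) = h for any window W. Both arms then show 5 (or 10) per 100 patient-months.

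**The case against.** **What a reader might infer, and why the documents do not support it**
- *That AEs are collected over different periods.* They are not. Section 8.3.1 sets one rule for both arms, and Table 2 continues collection after cross-over. Only tabulation differs.
- *That most placebo-arm patients stop contributing at cross-over.* No share is stated. Cross-over is optional and needs a separate consent (4.1.2).
- *That the combination is inflated by construction.* The interval from progression scan to cross-over counts in the placebo arm and can offset the whole 28-day tail. What remains depends mainly on how much post-PD treatment is used.
- *That the gap could be 19 or 26 points.* The same model with median PFS of 6 versus 3 months gives 36.2% versus 17.7% and 55.8% versus 30.1%. Cutting both arms at PD still leaves 28.7% versus 17.7% and 45.4% versus 30.1%, so 11 of the 19 points and 15 of the 26 come from longer progression-free treatment, as in any treat-to-progression trial.

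**Other points on the plan's side.** Safety is descriptive with no formal analysis (1.1). Exposure is summarised and first-6-week tables are planned. Appendix I 3.3 places most savolitinib hypersensitivity reactions in the first six weeks. Full AE detail is left to a SAP that is not in the documents, so the absence of exposure-adjusted rates from the protocol is not in itself a fault. A main table cut at PD would hide post-PD toxicity on the combination.

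**What stands.** These points limit the size, and they rule out replacing the planned tables. They do not remove the issue, because the window, the split at cross-over and the crude overview are all stated in 9.4.3. A separate exposure summary shows the imbalance but does not correct the percentages.

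**Conclusion.** The concern holds in a limited form. As written, section 9.4.3 can compare crude percentages over a longer window on savolitinib plus osimertinib than on savolitinib plus placebo for patients who cross over, which tends to disfavour the combination.

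Under the assumed inputs the artefact is about 5 to 8 points at 0.05 per month and 6 to 12 points at 0.10 per month. It falls to near zero with no post-PD treatment and cross-over at day 28. These figures rest on equal constant hazards, equal PFS, half of combination patients being treated past PD, and full cross-over uptake. None of these comes from the documents, so the direction is firmer than the size. Early-onset toxicities and the first-6-week tables are little affected. It is a cheap improvement to a descriptive analysis and bears on no efficacy conclusion.

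**What to change.** In 9.4.3, keep the planned crude tables and add two items for any AE, Grade 3 or higher AEs, SAEs and AEs leading to discontinuation:

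1. **Exposure-adjusted incidence by arm:** patients with a first event per 100 patient-months at risk. Time at risk for placebo-arm patients who cross over ends at the first cross-over dose.
2. **A supportive between-arm table with one common window:** first randomised dose to the earliest of investigator-assessed PD, first cross-over dose, or 28 days after last dose.

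The first item removes the artefact under a constant hazard and also handles unequal time to PD, which the second does not. Keeping the planned tables preserves the view of post-PD toxicity on the combination.

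The cost is one extra set of tables from data already collected. The rates assume a roughly constant hazard, so they should be read beside the first-6-week tables. No clinical rule changes.

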#### **9.4.4 Pharmacokinetic Analyses**

Pharmacokinetic analyses of the plasma concentration data for savolitinib, osimertinib and their metabolites (M2 and M3 for savolitinib; AZ5104 for osimertinib) will be performed by CPQP, AstraZeneca or a delegate on behalf of CPQP. The actual sampling times will be used in the parameter.

Where possible, the following PK parameters will be determined for savolitinib, osimertinib and their metabolites:

- After single dosing:  $C_{1h}$  and  $C_{3h}$  post-dose.
- After multiple dosing:  $C_{pre-dose}$ , and at  $C_{1h}$ , and  $C_{3h}$ , post-dose. Appropriate PK parameters such as  $AUC_{ss}$ ,  $C_{ssmax}$ ,  $T_{ssmax}$ ,  $CL_{ss}/F$  at Cycle 3, Day 1 may also be calculated for savolitinib, osimertinib and their metabolites. These parameters may be presented

separately for savolitinib plus osimertinib, savolitinib plus placebo and for patients who crossed over.

If possible, the time dependency of the PK on multiple dosing will be assessed by the calculation of the ratios of:

- $C_{3h}$  Cycle 2 Day 1/ $C_{3h}$  Cycle 1 Day 1
- $C_{pre-dose}$  Cycle 3 Day 1/ $C_{pre-dose}$  Cycle 2 Day 1
- $C_{pre-dose}$  Cycle 6 Day 1/ $C_{pre-dose}$  Cycle 2 Day 1

Where possible, the appropriate PK parameters will also be determined for the metabolites of savolitinib and osimertinib. The concentration data from this study may be combined with other studies to perform population PK analysis and if conducted, will be reported separately from the CSR.

#### **9.4.5 Other Analyses**

Biomarker analyses for the CSR will be described in the SAP.

Circulating-tumour DNA dynamics will be evaluated as a surrogate marker of clinical efficacy. For the secondary objective, the prevalence of ctDNA clearance of 6 weeks treatment with savolitinib and osimertinib will be determined.

The percentage change in EGFR mutation ctDNA allele frequencies at Week 6 will be obtained for each patient taking the difference between the allele frequency of EGFR sensitising mutations in ctDNA at Week 6 and the ctDNA at baseline divided by the allele frequency of EGFR sensitising mutations in ctDNA at baseline multiplied by one hundred (ie,  $[\text{Week 6 baseline}]/\text{baseline} \times 100$ ). Patients with undetectable EGFR mutations at baseline will be excluded from this analysis. Samples with undetectable EGFR mutations will be interpreted as 0% allele frequency so that the % change is 100%.

The absolute change in ctDNA at Week 6 will be obtained for each patient by the difference between the EGFR mutation ctDNA allele frequencies at Week 6 and at baseline.

[figure not shown]
Patients with detectable EGFR mutations at baseline and available data at 6-weeks will also be categorised into the following groups: (1) ctDNA clearance: defined by a 100% change in EGFR mutations in ctDNA (ie, undetectable at Week 6) and (2) ctDNA non-clearance: defined by a percent change in EGFR mutations in ctDNA less than 100% (ie, detectable at Week 6). Patients with undetectable EGFR mutations at baseline will be categorised as “uninformative.”

Handling of missing data will be described in the SAP.

The percentage change and absolute change at Week 6 in ctDNA from baseline will be summarised using descriptive statistics. Descriptive summaries showing the actual change and the percentage change from baseline in tumour size for each patient over time may be produced. Summary statistics of the categorised ctDNA groups will also be produced. Analysis will also be presented for patients in the Cross-over Analysis Set.

Waterfall plots showing the percentage change at Week 6 will be produced for the FAS and Cross-over Analysis Set. Spider plots showing the actual change and the percentage change from baseline in tumour size for each patient over time may be produced.

CCI

A large rectangular area of the document is completely redacted with a solid black box. The word "CCI" is visible in red text at the top left corner of this redacted area.

CCI

A horizontal rectangular area of the document is completely redacted with a solid black box. The word "CCI" is visible in red text at the top left corner of this redacted area.

CCI

A horizontal rectangular area of the document is completely redacted with a solid black box. The word "CCI" is visible in red text at the top left corner of this redacted area.

## 9.5 Interim Analyses

Prior to CSP V3.0, a non-comparative interim futility analysis for the savolitinib plus placebo arm was planned to occur after 20 patients overall (10 per arm) had the opportunity to be treated for 2 RECIST post-baseline scans (12 weeks). The outcome of the interim futility analysis was to be as follows:

- Stop further enrolment into the study if no responses are observed
- If true rate = 5%, there is a 59.9% probability of observing no responses.
- If true rate = 10%, there is a 34.9% probability of observing no responses.
- If true rate = 43%, there is a 0.4% probability of observing no responses.

Recruitment was to continue during the interim futility analysis.

If the decision was made by the IDMC that the study was futile, no new patients were to be enrolled into the study and all randomised patients were to be unblinded and those randomised to savolitinib plus placebo were to be given the opportunity to cross-over to savolitinib plus osimertinib (see Section 4.1.2).

The SAP will describe the planned analyses in greater detail.

Under CSP V3.0, as a result of AstraZeneca's decision to terminate study recruitment early, the planned interim futility analysis will not be performed and there will be no requirement for data review by the IDMC. Alternatively, following the termination of study recruitment, an initial DCO will occur to allow an early review of the data by AstraZeneca. The study will be unblinded after completion of data cleaning activities on the initial DCO data, and patients on savolitinib monotherapy (savolitinib plus placebo) will be given the opportunity to cross-over to the savolitinib plus osimertinib arm. If the investigator believes patients are gaining clinical benefit and patients have not reported PD, patients may continue to receive savolitinib monotherapy. All patients will be followed until the final analysis.

